**v. Sensitivity Analyses of endpoints**

To deal with missing data in the baseline assessment of the endpoint and to deal with missing data of the follow-up assessment of the endpoint, sensitivity analyses will be conducted, where missing follow-up values and baseline values will be multiple imputed using chained equations.

The missing data for the primary and secondary endpoints (as applicable what is actually missing, including baseline and follow-ups) are imputed using chained equations, 20 data-sets will be created. The equations include the baseline clinical characteristics, the non-missing primary from the previous follow-up assessment (baseline if none available). Endpoints are taken from baseline and all the follow-ups, as applicable (typically baseline, 180 days and 360 days).

Afterwards all sensitivity analyses are conducted on the 20 data-sets for the composite endpoint, The sensitivity analyses will be shown in the Supplementary Material following the same structure as the Tables 3 – 5.

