### **f. Sample size**

Sample size calculation is based on the on the data from the BASEL V study. A hypothesized 20%-decrease of the composite endpoint death or HF re-hospitalization at 180 days, will require 385 patients per treatment arm to obtain, with a probability of 80%, a log rank test result that is statistically significant at the 5%-level. In order to compensate for an expected 1-2% of patients in whom the primary endpoint could not be assessed at 180 days due to loss to follow-up or complete withdrawal of ICF, it was planned to enroll approximately 780 patients.

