### **m. Intention- To -Treat (ITT)**

The intention to treat population consists of all patients randomized. The primary and secondary endpoints of patients randomized to early goal-directed decrement of preload and afterload (intervention group) will be compared to the patients randomized to standard of care by the intention-to-treat principle.

Patients without a follow-up assessment at 6 months for the primary endpoint will be censored at the time of the last follow-up information available.

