### **v. Methods for handling missing data and sensitivity analyses**

Sensitivity analyses will be conducted in: patients without evidence of systemic, infection/inflammation at presentation (defined as CRP  $< 20$  mg/L), in patients without major protocol deviation and in patients enrolled in outside Europe and Central Europe.

To deal with data with  $> 10\%$  missing values, sensitivity analyses will be conducted using multiple imputations by chained equations methods and 20 data-sets will be created.

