**Table 1. Baseline Clinical Characteristics and Medical History**

	Total Patients (N=)	Intervention arm (N=)	Standard of care arm (N=)
Age – years ( $\pm$ SD)	XX $\pm$ XX	XX $\pm$ XX	XX $\pm$ XX
Male gender – no. (%)	xx (xx%)	xx (xx%)	xx (xx%)
BMI - kg ( $\pm$ SD)	XX $\pm$ XX	XX $\pm$ XX	XX $\pm$ XX
Cardiovascular Risk Factors:			
Diabetes mellitus – no. (%)	xx (xx%)	xx (xx%)	xx (xx%)
Dyslipidemia – no. (%)	xx (xx%)	xx (xx%)	xx (xx%)
Ever smoked – no. (%)	xx (xx%)	xx (xx%)	xx (xx%)
Hypertension – no. (%)	xx (xx%)	xx (xx%)	xx (xx%)
Structural heart disease:			
Hypertensive heart disease – no. (%)	xx (xx%)	xx (xx%)	xx (xx%)
Chronic Heart failure – no. (%)	xx (xx%)	xx (xx%)	xx (xx%)
CAD – no. (%)	xx (xx%)	xx (xx%)	xx (xx%)
PCI – no. (%)	xx (xx%)	xx (xx%)	xx (xx%)
Coronary Bypass – no. (%)	xx (xx%)	xx (xx%)	xx (xx%)
Myocardial infarction – no. (%)	xx (xx%)	xx (xx%)	xx (xx%)
Valvular replacement – no. (%)	xx (xx%)	xx (xx%)	xx (xx%)
Atrial Fibrillation – no. (%)	xx (xx%)	xx (xx%)	xx (xx%)
ICD/CRT – no. (%)	xx (xx%)	xx (xx%)	xx (xx%)
Chronic Comorbidities:			
COPD/ Asthma – no. (%)	xx (xx%)	xx (xx%)	xx (xx%)
Renal insufficiency – no. (%)	xx (xx%)	xx (xx%)	xx (xx%)
Peripheral vascular disease – no. (%)	xx (xx%)	xx (xx%)	xx (xx%)
Stroke – no. (%)	xx (xx%)	xx (xx%)	xx (xx%)
Pneumonia – no. (%)	xx (xx%)	xx (xx%)	xx (xx%)
Pulmonary embolism – no. (%)	xx (xx%)	xx (xx%)	xx (xx%)
Liver disease – no. (%)	xx (xx%)	xx (xx%)	xx (xx%)
Active malignancy – no. (%)	xx (xx%)	xx (xx%)	xx (xx%)
Symptoms at admission or shortly before			
NYHA class – no. (%)			
III	xx (xx%)	xx (xx%)	xx (xx%)
IV	xx (xx%)	xx (xx%)	xx (xx%)
Days with dyspnea – days ( $\pm$ SD)	XX $\pm$ XX	XX $\pm$ XX	XX $\pm$ XX
Chest pain – no. (%)	xx (xx%)	xx (xx%)	xx (xx%)
Nycturia – no. (%)	xx (xx%)	xx (xx%)	xx (xx%)
Weight gain – no. (%)	xx (xx%)	xx (xx%)	xx (xx%)

Orthopnea – no. (%)	xx (xx%)	xx (xx%)	xx (xx%)
Paroxysmal nocturnal dyspnea – no. (%)	xx (xx%)	xx (xx%)	xx (xx%)
Coughing – no. (%)	xx (xx%)	xx (xx%)	xx (xx%)
Sputum – no. (%)	xx (xx%)	xx (xx%)	xx (xx%)
Fever – no. (%)	xx (xx%)	xx (xx%)	xx (xx%)
Night sweats – no. (%)	xx (xx%)	xx (xx%)	xx (xx%)
Clinical examination:			
Heart murmur – no. (%)	xx (xx%)	xx (xx%)	xx (xx%)
Murmur radiation – no. (%)	xx (xx%)	xx (xx%)	xx (xx%)
Third heart sound – no. (%)	xx (xx%)	xx (xx%)	xx (xx%)
Positive HJR – no. (%)	xx (xx%)	xx (xx%)	xx (xx%)
Jugular ingurgitation – no. (%)	xx (xx%)	xx (xx%)	xx (xx%)

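### SAP 10.1.5 does not name the randomised arm or the stratification factors as imputation predictors; run as listed, the imputed comparisons lean toward no difference by up to the fraction missing

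*Combined protocol and SAP*

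**What the plan says.** SAP 10.1.5 (Sensitivity Analyses of endpoints) sets the scope: "The missing data for the primary and secondary endpoints (as applicable what is actually missing, including baseline and follow-ups) are imputed using chained equations". It then lists the predictors: "The equations include the baseline clinical characteristics, the non-missing primary from the previous follow-up assessment (baseline if none available"). The following sentence takes endpoints from baseline and all follow-ups, and gives baseline, 180 days and 360 days as the usual sequence. On use, it says "Afterwards all sensitivity analyses are conducted on the 20 data-sets for the composite endpoint", but it also places the results in the supplement, laid out like Tables 3 to 5, which cover secondary endpoints, quality of life and biomarkers.

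SAP 6.5 says that for data with more than 10% missing, "sensitivity analyses will be conducted using multiple imputations by chained equations methods and 20 data-sets will be created". It does not say which variables are meant, and 10.1.5 has no threshold.

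The baseline characteristics are those of SAP 7.1, Table 1 ("Baseline Clinical Characteristics and Medical History"). There the arm is a column heading and not a row; site and natriuretic peptide level do not appear.

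The main analysis does not impute. The SAP paragraph on the intention-to-treat population states: "Patients without a follow-up assessment at 6 months for the primary endpoint will be censored at the time of the last follow-up information available". The sample size section allows for "an expected 1-2% of patients in whom the primary endpoint could not be assessed at 180 days".

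**The concern.** An imputation model should contain every variable in the analysis that follows, above all the one whose effect is being estimated. If arm is left out and the other predictors are all baseline variables, missing outcomes in both arms are drawn from one common distribution. Randomisation balances the baseline variables, so they carry no arm effect into the imputed values.

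A sensitivity analysis is meant to show whether the result survives a different handling of missing data. With this built-in lean, a weaker imputed result might be read as fragility when it comes from the imputation model. If data are missing completely at random, the comparison of observed patients is unbiased, and imputing without arm would make it worse.

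**Working it through.** **1. The plan's own figure.** The only missing fraction in the documents is the 1-2% for the primary endpoint. Inflating 770: 770/0.99 = 778 and 770/0.98 = 786. The stated target of about 780 implies 1 - 770/780 = 1.3% loss, so it reproduces.

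**2. An event rate to work with (assumption).** No control event rate is stated, so 385 per arm cannot be reproduced from stated inputs. A 20% relative reduction from 50% to 40%, two-sided 5%, 80% power, needs 388 per arm (two proportions), 376 (Schoenfeld) or 381 (Freedman), all within 3% of 385. I use 50% and 40% for illustration only.

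**3. No arm, baseline predictors only.** Let a fraction f be missing completely at random in each arm. Missing patients in both arms receive the pooled rate (p_C + p_T)/2, so

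- p_C' = (1 - f)p_C + f(p_C + p_T)/2, and likewise for p_T';
- p_C' - p_T' = (1 - f)(p_C - p_T).

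At f = 2%: p_C' = 0.98 × 0.50 + 0.02 × 0.45 = 0.499 and p_T' = 0.98 × 0.40 + 0.02 × 0.45 = 0.401. The hazard ratio is approximated by ln(1 - p_T')/ln(1 - p_C').

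| f | Difference (points) | Relative risk | Approx. HR |
|---|---|---|---|
| 0 | 10.0 | 0.800 | 0.737 |
| 1% | 9.9 | 0.802 | 0.739 |
| 2% | 9.8 | 0.804 | 0.742 |
| 10% | 9.0 | 0.818 | 0.760 |
| 20% | 8.0 | 0.837 | 0.784 |

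This treats 180-day status as binary; it is an approximation to the time-to-event analysis.

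**4. No arm, but an earlier follow-up value in the equation.** For a continuous endpoint with the same arm effect δ at both visits, equal SDs and between-visit correlation ρ, the imputed values carry about ρδ. The retained share is therefore about 1 - f(1 - ρ). At f = 20% this is 0.90 for ρ = 0.5 and 0.96 for ρ = 0.8.

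For a cumulative event endpoint, take assumed rates of 46% and 36.8% at 180 days, then 20% and 16% by 360 days among those still event-free.

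- True 360-day rates: 0.46 + 0.54 × 0.20 = 0.568 and 0.368 + 0.632 × 0.16 = 0.469; difference 0.099.
- The pooled late rate is (0.108 + 0.101)/1.172 = 0.178. Imputed rates are 0.46 + 0.54 × 0.178 = 0.556 and 0.368 + 0.632 × 0.178 = 0.481; difference about 0.076, or 0.76 of the truth.
- The retained share is about 1 - 0.24f.

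**5. Simulation.** Share of the true difference retained. The continuous columns use 770 patients, 20 imputations and 600 replicates (Monte Carlo SE about 0.01); the event column uses one simulated population of 400,000.

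| f | No arm, no earlier follow-up | No arm, earlier value, ρ = 0.5 | No arm, earlier value, ρ = 0.8 | No arm, 180-to-360-day event | Arm included |
|---|---|---|---|---|---|
| 2% | 0.98 | 0.99 | 1.00 | 0.995 | 0.99 |
| 10% | 0.91 | 0.95 | 0.99 | 0.98 | 1.01 |
| 20% | 0.82 | 0.91 | 0.97 | 0.95 | 1.00 |
| 30% | 0.69 | 0.85 | 0.93 | 0.93 | 1.00 |

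The simulation agrees with the formulas. The full loss f applies where only baseline precedes the missing value, such as 48-hour BNP imputed from the baseline sample, or a 180-day value imputed from baseline. With an earlier follow-up value, the loss in these scenarios is roughly one fifth to one half of f. Naming the arm removes it.

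**The case against.** A reader might infer that every imputed comparison loses about the missing fraction. The documents do not support that. The listed predictors include the previous follow-up value, which brings part of the arm effect with it. Imputing a missing baseline value is a different problem, and where there is no true effect there is nothing to attenuate. This stands, and is why the bound is *up to* the fraction missing. The relief has limits: in the usual sequence given in 10.1.5, what precedes 180 days is baseline, unless the 90-day contact is used. Read literally, the predictor is also the previous primary endpoint, not the earlier value of the secondary endpoint being imputed.

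A reader might also infer that the check cannot confirm or challenge the main result. That fails as well. The main analysis censors, the expected loss is 1-2%, and the imputed results are supplementary.

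Three further defences carry weight. A list introduced as what the equations include need not be exhaustive, so the text shows that arm is unspecified, not that it will be excluded. The endpoint status taken from all follow-ups may already bring in some event information. Secondary analyses are declared explorative in SAP 6.6.4, with no significance threshold. None of these puts the arm into the equations.

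**Conclusion.** The point holds as a minor gap in specification with a known direction of bias. Run as listed, the imputed comparison understates a true difference by up to the fraction missing: by the full fraction with baseline predictors only, and by less with an earlier follow-up value.

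For the primary composite at 1-2% missing, the shift is 0.1 to 0.2 percentage points, or at most about 0.005 on the hazard ratio (0.737 to 0.742), which is negligible. At 10-30% missing, a secondary endpoint with only baseline predictors would lose about 10-30% of its true difference. Whether any endpoint reaches that level cannot be told from the documents.

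The figures assume data missing completely at random, equal missingness in both arms, 50% and 40% event rates, 10-30% secondary missingness, and the stated correlations and late event rates. None of these is in the documents. The direction of the bias does not depend on the particular rates chosen.

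**What to change.** In SAP 10.1.5, state that all imputation equations include the randomised arm and the stratification factors (site, pooled as in SAP 6.2, and natriuretic peptide stratum), or that imputation is done separately by arm. State also that for imputed time-to-event endpoints the equations include the event indicator and the Nelson-Aalen cumulative hazard.

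The cost is one sentence in the SAP and a few more variables in the imputation code. No new data are needed, and the main analysis is unchanged.

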**ee. Method for analysis**

**i. Binary data**

Binary data will be compared Intervention arm vs Standard of care using Fisher's exact test for 2 x 2 tables with two-sided p-values.

**ii. Count data**

Count data will be compared Intervention arm vs Standard of care using Pearson's chi-squared test with two-sided p-values.

**iii. Continuous scale data**

Continuous data will be compared Intervention arm vs Standard of care using Mann–Whitney U test with two-sided p-values.

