## Summary

**Background:** In contrast to treatment for chronic heart failure, which is based on several large prospective randomized controlled trials, treatment for acute heart failure is largely based on uncontrolled studies, clinical experience and expert opinion. Perhaps at least in part related to the uncertainties in the treatment of acute heart failure, outcome of patients with acute heart failure is extremely poor. Mortality is 50% at three years. More than 85% of patients with acute heart failure are treated in the non-ICU / CCU setting - the Emergency Department and the regular medical ward. Unfortunately, appropriate treatment is particularly ill-defined in this setting.

**Aim:** to test the hypothesis that a comprehensive approach using an early goal-directed decrement of preload and afterload with a target systolic blood pressure of 90 to 110 mm Hg by aggressive vasodilatation in patients with acute heart failure in the non-ICU setting is safe, and leads to a better clinical and economical outcome.

**Methodology:** This is a prospective, randomized, controlled multicenter study designed to enroll 770 patients presenting with acute heart failure at the emergency departments at the participating study sites. Patients will be randomly assigned 1:1 after stratification for site and B-type natriuretic peptide (BNP, NT-proBNP) levels to an early goal-directed therapy or standard care according to current guidelines. Early goal-directed therapy applies aggressive vasodilatation using sublingual and transdermal nitrates, hydralazine to avoid tolerance to nitrates, and rapid up-titration of angiotensin converting enzyme inhibitors and angiotensin II receptor blockers with a target systolic blood pressure of 90mm Hg to 110 mm Hg. Timing and dosing of diuretics and all other treatments are left to the discretion of the treating physician in both groups. The primary endpoint is death or heart failure readmission within 180 days. Secondary endpoints include the quantitative assessment of dyspnea, need for admission to the intensive care unit, surrogate markers like BNP or NT-proBNP, the digitally recorded third heart sound, renal function, time to discharge, functional status and quality of life, falls, total treatment cost, and cost-effectiveness. Patients will receive extensive clinical and economic follow-up of at least 360 days. Endpoints will be adjudicated by a clinical endpoint committee blinded to group assignment.

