## **8. Data Management and Statistics**

### **8.1 Data Management and Monitoring**

To appropriately describe the patient population, a dedicated case report form (CRF) including detailed patient history, physical examination, vital parameters during hospitalization and adverse events will be completed. Cost data will be converted in US dollar using the exchange rate of February 1st, 2009. All relevant data will be entered into SecuTrial® (interActive Systems GmbH, Berlin Germany) and Microsoft® Access® 2010 (Version 14.0.7162.5001, Microsoft®, USA). The use of these data is restricted to scientific purposes. Data management and monitoring support will be provided by the Clinical Trial Unit of the University Hospital Basel.

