## 1. Study synopsis

In contrast to treatment for chronic heart failure (HF), which is based on several large prospective randomized controlled trials, treatment for acute heart failure is largely based on uncontrolled studies, clinical experience and expert opinion. Perhaps at least in part related to the uncertainties in the treatment of acute heart failure, outcome of patients with acute heart failure is extremely poor with mortality arising to 50% at three years. As more than 85% of patients with acute heart failure are treated in the non-ICU / CCU setting - the Emergency Department and the regular medical ward-, it is still notable that appropriate treatment is particularly ill-defined in this setting.

Based on the aforementioned premise, our aim is to test the hypothesis that a comprehensive approach using an early goal-directed therapy with a target systolic blood pressure of 90 to 110 mmHg by aggressive vasodilatation in patients with acute heart failure in the non-ICU setting, is safe and has the potential to more rapidly improve dyspnea, to more rapidly and more extensively reduce heart failure disease severity as quantified by B-type natriuretic peptide levels and most importantly to reduce the occurrence of death and heart failure readmission. Due to the high cost associated with hospitalizations for heart failure, our study has the potential to define a novel treatment strategy that might also significantly reduce the treatment cost associated with acute heart failure.

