This trial was designed as a prospective, randomized, controlled multicenter study aimed to enroll 770 patients presenting with acute heart failure at the emergency departments at the participating study sites. Patients will be randomly assigned 1:1 after stratification for site and B-type natriuretic peptide (BNP, NT-proBNP) levels to an early goal-directed therapy or standard care according to current guidelines. Early goal-directed therapy aims to aggressive vasodilatation by using sublingual and transdermal nitrates, hydralazine (to avoid tolerance to nitrates) and rapid up-titration of angiotensin converting enzyme inhibitors and angiotensin II receptor blockers with a target systolic blood pressure of 90 mmHg to 110 mmHg. Timing and dosing of diuretics and all other treatments are left to the discretion of the treating physician in both groups. The primary endpoint is death or heart failure readmission within 180 days. Secondary endpoints include the quantitative assessment of dyspnea, need for admission to the intensive care unit, surrogate markers like BNP or NT-proBNP, the digitally recorded third heart sound, renal function, time to discharge, functional status and quality of life, falls, total treatment cost, and cost-effectiveness. Patients will receive extensive clinical and economic follow-up of at least 360 days. A clinical endpoint committee blinded to group assignment will adjudicate endpoints.

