### b. Secondary objectives

Secondary endpoints are:

- All-cause mortality at 180 days.
- HF re-hospitalization at 180 days.
- Death or re-hospitalization from all causes at 180 days.
- Need for ICU admission during initial hospitalization.
- Acute coronary syndrome during initial hospitalization.
- Symptomatic hypotension during initial hospitalization.
- B-type natriuretic peptide (BNP) and creatinine level at 48 h and at discharge.
- Changes in circumferences of both legs and central venous pressure during hospitalization.
- Change in patient-assessed dyspnea at 48 h and prior to discharge.
- Blood pressure course over the first 6 days.
- Time to disappearance of a third heart sound (if present initially).
- Time to discharge.
- In-hospital days for HF at 180 days and 360 days.
- Total treatment cost at 180 days and 360 days.
- Functional status at 180 days and 360 days.
- Quality of life (EQ-5D-3L) at 180 days and 360 days.
- Fractures due to falls within 180 days and 360 days.
- Death or HF re-hospitalization at 360 days.

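### No analysis rule names total treatment cost, and neither general SAP rule that could apply yields the mean cost difference that the economic aim needs

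*Combined protocol and SAP*

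**What the plan says.** **Endpoint and aim.** The secondary endpoint lists of both the protocol (2.2) and the SAP (2.2) include "Total treatment cost at 180 days and 360 days". The protocol Summary states the hypothesis that the strategy "is safe, and leads to a better clinical and economical outcome". The SAP synopsis says the strategy "might also significantly reduce the treatment cost associated with acute heart failure", and its list of secondary endpoints ends with "falls, total treatment cost, and cost-effectiveness".

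**Rules that could reach cost.**
- SAP 10.2.3 (Continuous scale data): "Continuous data will be compared Intervention arm vs Standard of care using" the Mann–Whitney U test, with a two-sided p-value. It asks for no effect estimate and no confidence interval.
- SAP 10.1.2 (Analysis of secondary endpoints): secondary endpoints follow the primary endpoint's approach, which 10.1.1 describes as Cox regression, Kaplan–Meier, hazard ratio and log rank.
- Protocol 8.2 lists the t-test and the Mann–Whitney test among several methods to be used as appropriate. It ties neither to cost.

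**Cost-specific text.** Protocol 8.1 says "Cost data will be converted in US dollar using the exchange rate of February" 1st, 2009. Beyond currency, no instruction on analysing cost was found. SAP Table 3 has no cost row, and no method is given for cost-effectiveness.

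**The concern.** A claim that a strategy saves money, and any cost-effectiveness ratio, rests on the arithmetic mean cost per patient: mean times number of patients is the total spent. Hospital costs are usually right-skewed, and a few long readmissions can carry much of the mean. A rank test asks a different question, namely whether a patient in one arm tends to cost more than a patient in the other. It supplies neither a difference in money nor an interval. A hazard ratio or log-rank p-value does not supply them either.

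So an analyst who follows the SAP has two conflicting general rules for cost, and neither output estimates the saving or feeds the cost-effectiveness analysis that the synopsis names. The estimator would then be chosen after the data are in. If cost spread differs between arms, the rank result could also miss a real mean difference or point the other way.

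**Working it through.** **1. Which rule applies.** Cost is continuous, so 10.2.3 points to Mann–Whitney. Cost is also a listed secondary endpoint, so 10.1.2 points to Cox and log rank. The SAP does not say which prevails. The protocol's t-test is not carried into the SAP. All routes in the SAP end without a mean difference.

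**2. Is there a figure to reproduce?** No. The documents give no mean, SD or target difference for cost. The 385 per arm in SAP 3.2 was derived for the primary endpoint and is used below only as the number of patients.

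**3. Assumptions for the illustration.** Lognormal costs, control median 10,000, two-sided 5% level, 385 per arm. None of the cost inputs comes from the documents. Formulas, with s the SD of log cost:
- mean = median × exp(s²/2)
- with equal medians, ratio of means = exp((s₁² − s₀²)/2)
- P(cost in arm 1 > cost in arm 0) = Φ((ln median₁ − ln median₀)/√(s₀² + s₁²)), which is what the rank test responds to

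**4. Equal medians, unequal spread.** The probability above is Φ(0) = 0.5 whatever the spread, so Mann–Whitney must sit near 5%.

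| log-SD | Means | Mean difference | Mann–Whitney rejects | Welch test of means rejects |
|---|---|---|---|---|
| 1.0 vs 1.05 | ratio exp(0.05125) = 1.053 | 5% | about 5% | not used here |
| 0.8 vs 1.0 | 13,771 vs 16,487 | 20% | 4.8% | 57% |
| 1.0 vs 1.2 | 10,000·exp(0.5) = 16,487 vs 10,000·exp(0.72) = 20,544 | 25% | 4.7% | 48% |

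**5. Other unequal-spread cases (log-SD 1.0 vs 1.2).**
- Equal means: the second median is 10,000·exp(0.5 − 0.72) = 8,025. Mann–Whitney rejects in 76% of trials, Welch in 5.8%.
- Median 15% lower, mean higher: 8,500·exp(0.72) = 17,463 against 16,487, or +5.9%. The rank probability is Φ(ln 0.85/√2.44) = Φ(−0.104) = 0.46, so the rank test favours the costlier arm. Mann–Whitney rejects in 51%, Welch in 5.7%.

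**6. Equal spread.** With no difference, both tests reject in about 5%. With costs 20% lower in one arm:

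| Common log-SD | Mann–Whitney rejects | Welch rejects |
|---|---|---|
| 0.8 | 96% | 90% |
| 1.0 | 85% | 67% |
| 1.2 | 70% | 42% |

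Here the two agree in direction and the rank test is the more powerful.

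Rejection rates come from simulation: 4,000 trials per setting in steps 4 and 5 and for the no-difference case, 3,000 for the 20% reduction in step 6.

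**The case against.** Four points deserve weight.

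- **Assignment to Mann–Whitney is an inference.** No section names a test for cost, and 10.1.2 is a competing rule aimed at secondary endpoints as such. This stands, and it is why the point is a missing cost analysis with two conflicting defaults rather than one wrong test.
- **The rank test is not useless for cost.** A reader might infer that it can neither support nor refute the economic hypothesis. The documents do not support that. If costs differ by a common factor, the rank test and the mean agree in direction and the rank test has more power (step 6). Disagreement needs different spread in the two arms. That is plausible for a strategy meant to change readmissions and time to discharge, but no document shows it. The 25% case is one assumed setting; a small difference in spread gives 5%.
- **Naming a test does not forbid reporting means.** SAP Table 3 shows mean ± SD for other continuous endpoints, and mean differences of change appear for quality of life and biomarkers. True, but cost has no row, and no mean difference with an interval is planned for it.
- **The stakes are limited.** SAP 6.6.4 calls all secondary analyses explorative and reads their p-values without a threshold. Cost-effectiveness appears in the summaries but not in either endpoint list. This lowers the priority. It does not supply the missing estimate.

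**Conclusion.** The point holds in this form: the plan sets an economic aim and a cost endpoint but specifies no cost analysis, and neither general rule that could apply estimates the mean cost difference. That part rests on the text alone and needs no assumption about the cost distribution.

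The practical size is unknown, because the documents give no cost figures. Under assumed lognormal costs with equal medians, Mann–Whitney stays at about 5% rejection while the means differ by anything from 5% (log-SD 1.0 vs 1.05) to 25% (1.0 vs 1.2). With equal spread there is no conflict in direction. The documents do not show that the planned test would mislead in this trial, only that it would leave the economic question without its estimate. The primary analysis and the sample size are unaffected. It is worth correcting, at low priority.

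**What to change.** In SAP 10.1.2 and 10.2.3, exempt cost from both general rules and state:

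1. Total cost at 180 and 360 days is compared by the arithmetic mean difference per patient, with a bootstrap 95% CI resampled within arm. Resample within site only after the pooling in SAP 6.2 (sites with fewer than 10 subjects), since very small strata understate the variance.
2. For cost-effectiveness, resample each patient's cost and outcome jointly.
3. Say how costs after withdrawal or loss to follow-up are handled. SAP 10.1.5 plans multiple imputation of missing endpoints as a sensitivity analysis, but does not say how a partly observed cost is treated.
4. Add a cost row to Table 3, with the mean per arm, the difference and its CI.
5. Keep Mann–Whitney as a supportive analysis only.

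The cost is a few sentences and a short program, with no change to the sample size or the primary analysis. The trade-off is less power than the rank test where spread is equal (67% against 85% at log-SD 1.0 in the illustration).
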